Patients will receive brochures for each medication class that they are prescribed, with subsequent brochures being mailed out 3 months after the previous one. We anticipate that less than 10% of participants are on 2 or more CNS medication classes. Additionally, we will mail all participants an antihistamine brochure because there is high utilization of over-the-counter antihistamine use, but prescriptions in automated data sources is low.

No other follow-up is conducted by the study team until it is time to pull automated patient data to measure outcomes as described in this application.

c. Flow diagram (if needed)

If the study design is complicated (i.e., has multiple populations, data sources, subject pathways, etc.), insert a flow diagram here or upload it as a separate document if the format is incompatible with this form.

NOTE: Update March 2021 - Due to initial delays due to COVID 19 and changes to procedures based on feedback from our intervention clinics (during both the first two recruitment waves and during our study overview sessions at clinics), our overall study time is going to be delayed significantly including pulling participants and collecting outcomes data, therefore we need to extend the date range for both sample identification and data collection by 1 year. This only applies to PHASE III (Study Intervention): The intervention will be rolled out monthly to clinics and persist for 12 months as depicted in the table below.

Clinic	Apr-2021	May-2021	Jun-2021	Jul-2021	Aug-2021	Sep-2021	Oct-2021	Nov-2021	Dec-2021	Jan-2022	Feb-2022	Mar-2022	Apr-2022	May-2022	Jun-2022	Jul-2022
1	x	x	x	x	x	x	x	x	x	x	x	x				
2		x	x	x	x	x	x	x	x	x	x	x	x			
3		x	x	x	x	x	x	x	x	x	x	x	x			
4			x	x	x	x	x	x	x	x	x	x	x	x		
5				x	x	x	x	x	x	x	x	x	x	x	x	
6				x	x	x	x	x	x	x	x	x	x	x	x	
7			x	x	x	x	x	x	x	x	x	x	x	x		
8					x	x	x	x	x	x	x	x	x	x	x	x
9					x	x	x	x	x	x	x	x	x	x	x	x

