From the intervention group at each clinic, we will sample the max cap number each month over the course of the intervention period opioid, z-drug, skeletal muscle relaxer, TCA, and prescription antihistamine users. We will prioritize which patient in the intervention group at each clinic gets mailed a brochure (and the class-concordant EBPO to the patient’s provider) as follows: Patients with a PC visit scheduled in the next 8-38 days will be prioritized in filling the max cap each month. This provides time for the patient and provider to receive and read the materials prior to the visit and optimizes the chances of a discussion about the medication being held as part of the visit (i.e., prepared patient and prepared provider as per the Chronic Care Model). If the max cap is not met for an intervention clinic in a given month, a random sample of the study intervention group will then be selected to fill the max cap for mailings that month.

Patients will receive only one brochure related to a given medication class during the intervention period. Patients taking >1 medication classes of interest will receive no more than one unique patient brochure every 3 months for a maximum of 4 brochures over the 12-month intervention period. If patients are using more than one of the five medication classes, the brochures mailed will be prioritized as 1) opioids; 2) benzodiazepines/Z-drugs; 3) muscle relaxants; 4) TCAs and; 5) antihistamines. Additionally, we will mail all participants an antihistamine brochure because there is high utilization of over-the-counter antihistamine use, but prescriptions in automated data sources is low.

One month after sending the brochure, patients will receive a postcard mailer with 3 self-reported questions regarding the type of brochure they received, it’s perceived helpfulness and whether the participant will initiate a conversation with their doctor.

Sending EBPOs to providers are triggered by the mailing of the patient brochure and will follow a similar logic. For the mailing of antihistamine brochures to patients without a prescription for antihistamines, we will have the clinic champion disseminate one final clinical pearl with a link to the EPBO for antihistamines to all providers.

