The intent of these materials is to start a conversation between the patient and provider that will improve health outcomes via dose reduction and/or discontinuation of the medication. The process by which deprescribing occurs will be determined by the provider and patient and with the involvement of a clinical pharmacist at the discretion of the patient’s PCP.

The process/algorithm for selecting which patients in the Intervention Group receive mailings each month is detailed below.

Opt-Out Protocol (July 2020-October 2020)

1. Every month after clinic launch through 12-months post, update the current chronic high-risk medication use among the Intervention Group.
2. Create a pool of eligible patients to mail to from each clinic's Intervention Group. Pool includes:
 - a. Current chronic users of 5 high-risk medication classes of interest with no prior mailing for that medication class. Multiple records per person.
 - i. Sort by order of priority of target medication classes (opioid, benzo/z-drug, muscle relaxant, tca, antihistamine) and keep only one record per patient if multiple. For example, a current chronic user of opioids and benzos with no prior mailings of either would go into the mailing selection pool as an opioid user.
 - b. No mailings in the prior 3 months.
 - c. Exclude anyone who has been withdrawn from the study on file as deceased, or previously had a "bad address".
3. Sample eligible patients for mailings (set max cap at 15% of sample for that clinic).
 - a. Prioritize those with a PC appointment to a provider in that clinic in the next 8-38 days.
 - i. FaxEBPO to provider the visit is **scheduled with**
 - b. Prioritize those with no prior mailings to fill up the rest of the max cap for mailing.
 - i. Mail to the most frequent prescriber of the medication (prior 12-months).

Waiver of Consent/HIPAA Authorization Protocol (December 2020-)

1. Every month after clinic launch through 12-months post, update the current chronic high-risk medication use among the Intervention Group.
2. Create a pool of eligible patients to mail to from each clinic's Intervention Group. Pool includes:
 - a. Current chronic users of 5 high-risk medication classes of interest with no prior mailing for that medication class. Multiple records per person.

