 - i. Sort by order of priority of target medication classes (opioid, benzo/z-drug, muscle relaxant, tca, antihistamine) and keep only one record per patient if multiple. For example, a current chronic user of opioids and benzos with no prior mailings of either would go into the mailing selection pool as an opioid user.
 - b. No mailings in the prior 3 months.
 - c. Exclude anyone who is on file as deceased, or previously had a "bad address".
3. Sample eligible patients for mailings (set max cap at 15% of sample for that clinic).
 - a. Prioritize those with a PC appointment to a provider in that clinic in the next 8-38 days.

- i. Send staff message to with link to EPBO to provider the visit is scheduled with
 - b. Prioritize those with no prior mailings to fill up the rest of the max cap for mailing.
 - i. Send staff with message with link to EPBO to the most frequent prescriber of the medication (prior 12-months).
- 4. After all participants have received their mailing, mail antihistamine brochure to everyone
 - a. No mailings in the prior 3 months.
 - b. Exclude anyone who is on file as deceased, or previously had a “bad address”.
 - c. Exclude anyone who received an antihistamine mailing already due to chronic use of prescription antihistamines

f. Alternative Procedures

Guidance: If there are alternative treatments or procedures that might be advantageous to the participant it should be included in the consent form.

Are there alternative procedures or treatments that might be advantageous to the participant?

☐ YES ☒ NO

If YES, please describe briefly.

[]

g. Denial of Procedures or Treatment

Guidance: If participants are denied access to certain procedures or treatments during the course of the study, this information must be included in the consent form.

Are there any procedures or treatments that the participant will be denied access to?

☐ YES ☒ NO

If YES, please describe briefly.

[]

h. Relationship to Clinical Care

If this study is a clinical trial, pragmatic trial, or a study that in any way interfaces with clinical care, please describe exactly which procedures will be conducted for the research as opposed to procedures the subjects would undergo (in the exact manner described in the protocol, if there is a protocol) even if they were not participating in the study.

This is applicable to PHASE III (Intervention) ONLY:

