The intervention does not directly interface with clinical care. We will send, via staff message with a url to the EBPOs to providers whose patients receive educational brochures for the target medication classes. Our goal is to educate patients and providers on the risks of these medications for older people, to provide guidance about safer alternatives, and to share information about safe deprescribing. The conversations and actions taken by providers and patients as a result of the intervention materials will be determined by the provider and patient. Our materials may result in increases in PC visits at these clinics and potentially referrals to pharmacy for assistance with deprescribing. The delivery system is aware and onboard with this potential uptick in services because it is a KPWA goal to reduce use of these medications by elderly enrollees. We set our max cap of mailings each month to a number that is consistent with delivery system capacity (per conversations and approval of delivery system leaders).

i. Study Records in EHR

Guidance: If study records will be placed in EHR, this information must be included in the consent form.

Will you place a copy of study information (e.g., study participation, study-initiated test results, messages to physicians, genetic test results, incidental findings) in the subject's medical record?

☐ YES ☒ NO

If YES, describe here what information will be put in the subject's medical record.

| |

j. Return of Results/Lab Tests to Subjects or Providers

Guidance: Sharing results with subjects and/or providers must be described in the consent form.

Will study results, or individual subject results, such as results of standard or research lab tests (and genetic tests) be shared with subjects or their providers?

☐ YES ☒ NO

If YES, please describe briefly.

| |

k. Patient Initiated Withdrawal

Describe procedures that will be followed when subjects withdraw from the research, including withdrawal from intervention but continued data collection.

Phase II (Focus Group): Because participation in Phase II involves attending a 1-time focus group, the only option for withdrawing from the study is to leave in the middle of the focus group. Participants are allowed to do this if they choose. We will still use any data we have collected in the focus group up to the time they choose to leave.

Phase III (Trial):**Opt-Out Protocol (July 2020-October 2020)**

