If a participant in Phase III withdraws from the study, we will remove his/her study ID from future data pulls but will keep data previously obtained. This means that although they received the initial brochure, we will not mail future patient brochures (or accompanying EBPOs to their providers) to patients who opt out/withdraw from the study.

Waiver of Consent/HIPAA Authorization Protocol (December 2020-)

Participants will not be able to withdraw from the study. We have included clarifying language in the notification of study letter that they may receive multiple informational brochures and postcards and that they do not have to act on the materials. We have requested a waiver of consent and HIPAA authorization for the collection of the EMR from which participants cannot opt out of.

|

l. Investigator Initiated Withdrawal

Describe any anticipated circumstances under which subjects could be withdrawn from the research without their consent.

| Not applicable for this study. |

m. Orderly Termination

Describe any procedures for orderly termination of the study, if applicable.

| Not applicable |

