KPWA VDW	All healthcare utilization for the outcomes (falls, MVC, overdose, ADWEs) such as primary care visits, specialty visits, emergency department visits, inpatient stays, nursing homes..	6/1/2019 – 9/30/2024
KPWA VDW	
Pharmacy dispensing data (drug name, date of dispensing, strength, quantity, days supply, provider id, NDC) for the following intervention target medication classes: benzodiazepines, z-drugs, opioids, muscle relaxants, antihistamines, tricyclic antidepressants.
 
In addition, the following medication classes are needed to examine whether target medications were substituted with equally unsafe medications as a result of the intervention: Gabapentinoids, other sedative hypnotics, other antidepressants, steroids, second generation antihistamines, NSAIDs, topical pain medications, and injectable pain medications (e.g., cortisone injection)
	6/1/2019 – 9/30/2024
CESR VDW	CESR Med Order Table information (e.g. instruction for usage, prescription date, medication type)	6/1/2019 – 9/30/2024
KPWA VDW	Demographics (e.g., age, sex, gender, race, marital status)	6/1/2019 – 9/30/2024
KPWA Clarity	Patient reported outcome scores and dates questionnaire was administered – pain (PEG), anxiety (GAD), depression (PHQ-9), insomnia (ISI)	6/1/2019 – 9/30/2024
KPWA clinical notes in the EMR (extracted with	Mention of symptoms (yes, no) or scores for symptom questionnaires on pain, anxiety, depression, and insomnia. Date of	6/1/2019 – 9/30/2024

natural language processing)	mention or administration of questionnaire.	
KPWA EMR	Date and provider of scheduled primary care, physical therapy and mental health visits	6/1/2019 – 9/30/2024
KPWA EMR	Referrals to pharmacy (y, n) and date Referrals to acupuncture (y,n) and date Referrals to COMET (y,n) and date Referrals to pain clinic (y,n) and date Referrals to massage (y,n) and date Referral to mental health (y,n) and date Referrals to sleep clinic (y,n) and date Referrals to pain clinic (y,n) and date	6/1/2019 – 9/30/2024
KPWA VDW	Provider ID, Specialty, Provider Type, primary practice clinic. Data collected so that we can determine who the patients' PCP is for Epic Staff Messaging the EBPO to the correct provider).	Intervention Launch to Intervention End

e. Other Data

Describe any other data collection activities not already mentioned above. For example, using aggregate data to describe the study sample (provide a table for this activity).

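### The waiver-protocol mailing algorithm never re-applies the clinical exclusions after roll-out, so a chronic user who enters hospice, or newly meets another clinical exclusion, can still be sent a taper brochure

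*Combined protocol and SAP*

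**What the plan says.** Sections 3.3.a and 7.1.e say that the sample for each clinic is identified once, at roll-out (or the matched date for a control clinic), and then does not change. The exclusions in 3.3.b belong to that single draw. For the waiver protocol they include dementia, skilled nursing residence, metastatic cancer in the prior 12 months, hospice or palliative care, and an opioid use disorder code. The last of these is not limited to opioid users.

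The monthly algorithm for the waiver protocol (7.1.e) works as follows:

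- Step 1 refreshes current chronic use. Section 5.2.a likewise mentions only the medication lists.
- Steps 2.a and 2.b admit current chronic users with no earlier mailing for that class and no mailing in the past 3 months.
- Step 2.c reads "Exclude anyone who is on file as deceased, or previously had a" bad address.
- Step 4 sends the antihistamine brochure to everyone else. It uses the same death and address filter and also drops those already sent that brochure.

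On repeat mailings, 7.1.e says "Patients will receive only one brochure related to a given medication class during the intervention period", and 2.3.b says "We anticipate that less than 10% of participants are on 2 or more CNS medication classes". On leaving the study, 7.1.k (waiver protocol) says "Participants will not be able to withdraw from the study", and 7.1.l answers "Not applicable for this study".

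**The concern.** At entry the plan treats these patients as unsuitable for the intervention. After roll-out nothing in the written steps keeps the intervention from them. A patient whose opioid or sedative has become part of end-of-life care is still a chronic user and still due a brochure. So is a patient with a newly recorded opioid use disorder. The brochure carries a sample taper schedule, and a message with the matching evidence-based pharmaceutical opinion (EBPO) goes to a provider.

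Section 7.3.c itself names withdrawal events as a possible side effect if participants taper, and it plans chart review of serious events among opioid and benzodiazepine users. Such review detects harm but does not prevent the mailing. Sections 9.2 and 9.3 plan no data safety monitoring plan or board.

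What is at stake is avoidable exposure of a few frail patients. Power and the validity of the comparison are not in question.

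**Working it through.** **Is there a re-check anywhere?** Four places could supply one.

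1. *Steps 1, 2.a-c and 4.a-c of 7.1.e.* They cover medication use, earlier mailings, spacing, death and address. None covers a clinical exclusion.
2. *The word eligible in steps 2 and 3.* The pool is defined by items a to c, so the word adds no further filter.
3. *The waiver-protocol data table in 4.2.* It lists hospice admissions, nursing-home and hospice referrals, tumor registry, opioid-use diagnoses and dementia drugs to 30 June 2023. The last intervention month in the 2.3.c schedule is July 2022, so a re-check is feasible. No step calls for one.
4. *Recurring files in 4.1.* The regular feed concerns enrolment in the SMART and STRIPE studies, not clinical status.

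**How long is a patient exposed?** The plan gives no figure to reproduce. The inputs are:

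- about 5,000 trial participants (3.1); half, 2,500, is assumed for the intervention arm;
- a cap of 15% of the clinic sample per month (7.1.e, step 3);
- an assumption that the first round falls at month 0 and each cap is filled with first mailings.

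Rounds needed = 1/0.15, rounded up = 7. That is 15% in each of months 0 to 5 and the last 10% in month 6.

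Mean wait = 0.15 × (0+1+2+3+4+5) + 0.10 × 6 = 2.25 + 0.60 = 2.85 months.

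**How many patients?** The documents give no incidence. Assume an annual rate r for all the clinical exclusions combined.

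Newly flagged before a first class brochure = 2,500 × r × 2.85/12:

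| Assumed r per year | Patients |
|---|---|
| 0.5% | 3.0 |
| 1% | 5.9 |
| 2% | 11.9 |
| 5% | 29.7 |

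**Sensitivity to the cap.** Section 7.1.e also states a cap of 35-95 per clinic per month.

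- All nine clinics at 35: 315 a month, 8 rounds. Mean wait = (315 × 21 + 295 × 7)/2,500 = 3.47 months, which gives 3.6 to 36 patients at 0.5-5%.
- All nine clinics at 95: 855 a month, 3 rounds. Mean wait = (855 × 1 + 790 × 2)/2,500 = 0.97 months, which gives 1.0 to 10 patients.

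**Second class brochures.** Fewer than 10% of patients, so at most 250, are expected on two or more classes. With a gap of exactly 3 months, 250 × r × 3/12 = 0.3 to 3.1 at 0.5-5%.

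Patients who die or stop the medication are already removed by the written steps. They are not subtracted here, so the counts are upper bounds in that respect.

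**The case against.** The strongest reply is that this is a low-intensity educational mailing with several buffers, and that all it needs is a clarification. Deprescribing is decided by provider and patient (7.1.e, 7.1.h). The notification letter tells patients they need not act (7.1.k). The taper is only a sample, with repeated advice to talk to providers. The EBPO link goes to the provider with the scheduled visit or to the drug's most frequent prescriber over the prior 12 months, who can override it. One brochure per class closes the gap for most patients early. All of this stands and limits the harm. None of it stops the mailing, and the most frequent past prescriber may not be the clinician now managing end-of-life care.

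Four stronger readings are tempting and are not supported:

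- *That the static sample is the error.* It is a sound basis for analysis as assigned. The gap is in delivery only.
- *That the waiver removed a safeguard.* The opt-out version said "Exclude anyone who has been withdrawn from the study on file as deceased", so it also dropped withdrawn patients, but it had no clinical re-check either. Leaving that term out follows from the end of withdrawal. The answers in 7.1.k and 7.1.l concern leaving the research, and they say nothing on whether a mailing may be held.
- *That all 3-30 patients face the end-of-life or opioid use disorder harm.* The assumed rate pools five exclusions, so that subset is smaller by an unknown amount.
- *That step 4 can be counted in the same way.* It comes after all other mailings and carries its own 3-month rule, so the documents fix no mailing date on which to base a count. Patients without a prescription antihistamine also trigger no patient-specific EBPO.

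A re-check may also be done in practice. The documents cannot settle that.

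**Conclusion.** The point holds for the algorithm as written. A current chronic user who newly meets a 3.3.b clinical exclusion while a class brochure is due stays in the pool, and no other part of the plan takes that patient out. The plausible size is small: roughly 3-30 patients before a first class brochure. That rests on about 2,500 intervention patients, the 15% cap and an assumed 0.5-5% a year for all the exclusions together. Across the alternative cap it is about 1-36. Neither the rate nor the drug-class mix is in the documents, so the true number is unknown. The case rests on exposure that is foreseeable, that the plan's own criteria mark as unsuitable, and that is cheap to avoid. It should be changed, but it does not threaten the trial's conclusions.

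**What to change.** At steps 2.c and 4.b, before each mailing, re-run the 3.3.b clinical exclusion flags from the sources used at entry. Hold the brochure and any linked EBPO for anyone flagged. For a new opioid use disorder code, apply the plan's own all-class exclusion or, at minimum, hold the opioid brochure. Confine the re-check to clinical flags. Enrolment in COMET, the pharmacy opioid-dose initiative, after roll-out is not one, and it may follow from the intervention: 7.1.h says "Our materials may result in increases in PC visits at these clinics and potentially referrals to pharmacy for assistance with deprescribing", and 7.3.d collects "Referrals to COMET (y,n) and date".

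Protect the comparison while doing this. Section 2.2.d starts follow-up when a mailing is sent, with a mimicked date in usual care. A held patient would then have no start date in the intervention arm, while a similar control would have one. So make the monthly draw first, record the draw date as the start of follow-up, count the draw as that class's mailing, and only then hold the materials. Make the mimicked draw in usual-care clinics by the same rule. Keep every patient in the static cohort and analyse as assigned.

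The cost is minor programming, a few unused mailing slots, and a start date set by the draw rather than by an actual mailing for the few patients held. The 4.2 table does not name dementia diagnosis codes or palliative-care encounters, so the sources used for those at entry need to be stated. If a re-check is already done, writing it into steps 2.c and 4.b, with the start-date rule, is enough.
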